3.1.5 Safety Follow-up Period

The safety follow-up period follows the treatment period with the final visit, per schedule of assessments, up to a maximum of 19 days after the EOS visit.

3.1.6 Reference Dates (Relative Study Day)

Per the aforementioned periods, study day will be calculated relative to the reference date and will be used to show start/stop day of assessments and events in patient data listings.

Reference date: Defined as date of randomisation (Visit 2).

- If the date of the assessment/event is on or after the reference date, then:

Relative study day = (date of event – reference date) + 1

- If the date of the assessment/event is prior to the reference date, then:

Relative study day = (date of event – reference date)

Subsequently, randomisation as disposition event occurs on relative study Day 1 and Day 0 is not defined.

In the situation where the assessment/event date is partial or missing, relative study day and corresponding durations will appear partial or missing in the patient data listings.

3.1.7 On- and Off-treatment Periods

For safety and limited efficacy analyses, two additional periods are defined for analysis purposes:

3.1.7.1 On-treatment Period

The on-treatment period is defined as the period from first dose of study treatment up to and including last dose of study treatment + 7 days.

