3.9.3 Procedures for permanent discontinuation of a subject from investigational product

At any time, patients are free to discontinue IP, without prejudice to further treatment. A patient that decides to discontinue IP will always be asked about the reason(s) and the presence of any AEs. Adverse events (AEs) will be followed up (see Section [6](#)) and all IPs should be returned by the patient. Patients permanently discontinuing IP should always be asked to continue the regular visits. It is essential to collect as much data as possible for all patients throughout the study and especially all potential endpoint events. Complete

withdrawal from the study (withdrawal of consent) has a direct negative impact on the potential validity of all study data and should be avoided wherever possible.

If patients are not willing to come back to study visits, the sites are encouraged to investigate patient barriers to study visit compliance and discuss with the CRA if there is any alternative follow-up schedule which can meet patient expectations. Prior to implementing alternative follow-up schedules, AstraZeneca approval must be granted.

If a patient is withdrawn from study, see Section 3.10.

3.9.4 Procedures and guidance for temporary IP discontinuation in relation to coronavirus disease 2019 (COVID-19)

If a patient is diagnosed with COVID-19 or is suspected to have COVID-19 and an AE/SAE is reported (see Section 6.3.10), the Investigator should determine whether the patient's IP administration should continue or be temporarily discontinued. Patients who are discontinued from IP due to COVID-19 are to remain in the study whenever possible for safety follow-up.

In case a patient is unable to attend on-site visits for undergoing safety-related assessments as detailed in the Schedule of Assessments (Table 2), due to local public health rules, patient inability or patient/caregiver decision, the patient must be temporarily discontinued from IP, unless the safety-related assessments (including vital signs, physical examination, blood samples for safety laboratory assessments, urine for urinalysis, eDevice review, ECGs, VOCs, and recording of concomitant medications and AEs) can be performed at the patient's home and/or local laboratories or other local facilities by delegated site staff.

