4.2.5.1 Study Treatment Exposure

Total duration of study treatment exposure (days) by dose level and overall dose level (includes missed exposure days due to study treatment interruptions):

- Exposure (days) = (date of last dose of double-blind randomised study treatment – date of first dose of double-blind randomised study treatment) + 1

Where:

Date of first dose of double-blind randomised study treatment equals:

- Variable: *Start date of study drug administration*: Based on the EX eCRF, earliest administration date, at or after randomisation (Visit 2), at a given dose level and for each dose level received.
- By overall dose level: Overall earliest of the aforementioned first dose of study treatment administration dates, over all dose levels received.

Date of last dose of double-blind randomised study treatment equals:

- Variable: *End date of study drug administration*: As captured on the EX eCRF and is the latest administration date, on or after randomisation (Visit 2), at a given dose level and for each dose level received regardless of temporary study treatment administration discontinuation (study treatment interruptions).
- By overall dose level: Overall latest of the aforementioned last dose of study treatment administration dates, over all dose levels received. Patients may prematurely discontinue study treatment administration whilst continuing with scheduled assessments in the double-blind randomised treatment period. DOSDISC eCRF collects the variable, *date subject discontinued IP*. This date should equal the overall date of last dose of study treatment as captured on the EX eCRF but can be used in conjunction with EX data to accurately identify the overall date of last study treatment administration over all dose levels received in the double-blind randomised treatment period.

Total exposure years (across patients in a given treatment group) is defined as the sum of total double-blind randomised study treatment exposure (days) by overall dose level, including missed exposure days due to study treatment interruptions, for all patients in a given treatment group and is expressed in years as follows:

- Total exposure years (across patients) = Sum of (total study treatment exposure [days] by overall dose level)/360

Where:

Year = 360 days. .

Actual study treatment exposure (days) by dose level and overall dose level follows the same approach, however excludes all missed exposure days due to study treatment interruptions.

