4.2.6.3 Sensitivity Analyses

Sensitivity analyses to assess the robustness of the primary analysis results to missing data as outlined in [Appendix E Accounting for Missing Data](#), may be conducted utilising the FAS, unless otherwise specified, depending on the amount of missing data due to patients who prematurely discontinue study treatment and/or study participation.

In addition to the sensitivity analyses outlined in [Appendix E Accounting for Missing Data](#), the following analyses will also be performed:

- 1 The primary analysis will be repeated including only data from patients whilst being on study treatment ie, excluding data once patients discontinue from study treatment. For this analysis the patient's observed follow-up time will correspond to their actual "on-treatment" period defined as the period from first dose of study treatment (ticagrelor or

placebo) up to and including last dose of study treatment + 7 days. Refer to Section 3.1.7.1.

- 2 The primary analysis will be repeated where the response variable is the number of VOC events that occur during the defined treatment period, irrespective of the number of days between the onset of events.
- 3 The analysis will be repeated by replacing the factor for IxRS baseline hydroxyurea use (Yes/No) with a more inclusive indicator for hydroxyurea use defined as a combination of (a. and/or b.):
 - (a) IxRS baseline hydroxyurea use (Yes/No) **AND/OR**
 - (b) Hydroxyurea use:
 - (i) Start date after randomisation (Visit 2) AND
 - (ii) Duration of hydroxyurea use of at least 6 months during the study (latest stop date of hydroxyurea use record – earliest start date of hydroxyurea use record AFTER randomisation [Visit 2] + 1 [converted to months] \geq 6 months).
Where:
In case of ongoing medication use, study completion date, as collected on the disposition eCRF, or date of premature study discontinuation will be used to impute the latest stop date of hydroxyurea use in order to derive duration (months) within the context of the study.
If both these criteria (i) and (ii) are met the value will be “Yes”, otherwise it will be “No”.
- 4 The primary analysis will be repeated using the PP analysis set.
- 5 The primary analysis will be repeated for the following combination of covariates, if there are at least 5 patients within each stratum:
 - (a) Treatment group, baseline hydroxyurea use (Yes/No), age group at randomisation (Visit 2) (\geq 2 years to < 12 years, \geq 12 years to < 18 years)

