- Efficacy estimand: What would the outcome have been if all patients had stayed on study treatment: This will be estimated using the primary analysis method but including only data from patients whilst being on initial randomised study treatment, and assuming MAR subsequently.
- Effectiveness estimand with assumed loss of effect post-discontinuation of ticagrelor: This will be estimated using the pDRMI and DRMI controlled imputation approaches including only data from patients whilst on study treatment.

Therefore, the primary analyses and sensitivity analyses will be repeated including only data from patients whilst being on initial randomised study treatment ie, excluding data once patients discontinue from randomised study treatment.

A summary of reasons for patients withdrawing from the ticagrelor and the corresponding treatment group used to calculate the imputation VOC event rate under MAR, DRMI and pDRMI are presented in [Table 6](#). As for patients who withdraw from the study, a review of each patient who discontinued double-blind randomised study treatment will be carried out prior to database lock and routine study unblinding, where the default assumptions for pDRMI and DRMI as described in [Table 5](#) may be changed. Again, a list of these patients and the assumptions made under pDRMI and DRMI will be documented prior to database lock and routine study unblinding.

Table 6 **Reasons for patients discontinuing from the ticagrelor and the corresponding treatment group used to calculate the imputation VOC event rate under MAR, pDRMI and DRMI**

Reason for discontinuation of treatment^a	MAR	pDRMI	DRMI
Subject decision	Ticagrelor	Based on review prior to study unblinding	Based on review prior to study unblinding
Adverse event	Ticagrelor	Placebo	Placebo
Severe non-compliance to protocol	Ticagrelor	Ticagrelor	Placebo
Condition under investigation worsened	Ticagrelor	Placebo	Placebo
Development of study-specific discontinuation criteria	Ticagrelor	Placebo	Placebo
Subject lost to follow-up	Ticagrelor	Ticagrelor	Ticagrelor
Other ^b	Ticagrelor	Based on review prior to study unblinding	Based on review prior to study unblinding

^aAll patients withdrawing from placebo have VOC event rate imputed using the placebo treatment group rate.

^bAll patients withdrawing for a COVID-19 related reason, regardless of which category of reason is collected for them, will be reviewed prior to study unblinding

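### The on-treatment efficacy analyses count temporary treatment stops as time on drug whenever dosing later resumes, which does not match the estimand they are meant to serve

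*SAP*

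**What the plan says.** SAP 3.1.7.1 sets one unbroken window, which SAP 3.1.7 assigns to safety and some efficacy analyses: "The on-treatment period is defined as the period from first dose of study treatment up to and including last dose of study treatment + 7 days". SAP 4.2.5.1 takes the last dose as the latest administration date, "regardless of temporary study treatment administration discontinuation (study treatment interruptions").

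Two sets of efficacy analyses rest on this window:

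- Sensitivity analysis 1 in SAP 4.2.6.3: "The primary analysis will be repeated including only data from patients whilst being on study treatment ie, excluding data once patients discontinue from study treatment". Its offset is the length of the on-treatment period.
- The on-treatment analyses in SAP Appendix E. The first is described as "Efficacy estimand: What would the outcome have been if all patients had stayed on study treatment" and is estimated with the primary model on data from the initial randomised treatment only. The effectiveness estimand applies the reason-based imputations (pDRMI and DRMI) to the same data. Appendix E gives no other definition of on-treatment time.

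Protocol 3.9.2 foresees temporary stops for low platelets, surgery or invasive procedures, prohibited medication and COVID-19. Under Protocol 3.9.4, when a child cannot attend on-site safety assessments, "the patient must be temporarily discontinued from IP, unless the safety-related assessments" can be done at home or locally. Dosing may restart later.

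SAP 4.2.5 and 4.2.5.1 already derive missed exposure days from the EX eCRF, and an actual exposure that leaves them out. These feed the exposure and compliance summaries only. Nothing removes gap days, or the VOCs in them, from the on-treatment efficacy analyses.

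**The concern.** The efficacy estimand asks what would have happened had nobody come off drug. The window removes only the time after the final dose, so a gap in the middle stays in, with its days in the offset and its VOCs in the count. Whether a given off-drug day counts as on-drug then depends on a later event: one further dose brings the whole gap in, and no further dose cuts it after 7 days. Two children with the same gap are treated differently.

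This matters for interpretation. The treatment-policy primary analysis is meant to carry the effect of stops. The on-treatment analyses are there to show the effect without them, and Appendix E presents the efficacy estimand as the easiest to interpret. If both share part of the same dilution, close agreement between them could be misread as showing that interrupted treatment does not explain a weak result. Under missing-at-random imputation, a diluted ticagrelor rate would also carry into the imputed counts.

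**Working it through.** **Inputs.** Protocol 8.2: negative binomial shape 0.8, placebo rate 2.0 per year, 50% reduction, 154 patients randomised 1:1, minimum follow-up 12 months and mean 18, two-sided 5%. SAP 4.2.5.1 example: 9 missed days out of 238. Protocol 1.2.2: ticagrelor acts reversibly.

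**1. The plan's power figure.** Read shape 0.8 as dispersion k = 1/0.8 = 1.25. Information per patient is μt/(1 + kμt). At t = 1.5 years:

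- placebo: 3/(1 + 3.75) = 0.632
- ticagrelor: 1.5/(1 + 1.875) = 0.522
- with 77 per arm, SE = √[1/(77 × 0.632) + 1/(77 × 0.522)] = 0.213
- ln 2/0.213 − 1.96 = 1.29, so power is 90.2%

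With follow-up spread uniformly over 1–2 years the formula gives 89.95%, and a simulation of 2,000 trials gives 90.6%. The stated figure of about 90% is reproduced.

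**2. Dilution.** Let f be the share of ticagrelor window time that is off drug. Assume no residual effect in that time, and gaps unrelated to VOC risk. Ticagrelor patients then have rate RR × λ for a share 1 − f and rate λ for a share f, while the placebo rate is λ throughout:

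observed RR = RR(1 − f) + f = RR + (1 − RR)f

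**3. Results.** In the SAP example the gap is 17–25 November 2019. A 7-day extension from 16 November covers 7 of the 9 days, leaving 2: 2/238 = 0.84%, against 9/238 = 3.8% with no extension. The 238 days cover one dose level only and that patient carried on at the next, so the share of the full window is smaller still.

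| Case | f | RR if true 0.50 | RR if true 0.80 | Power, 154 patients, true 0.50 |
|---|---|---|---|---|
| SAP example, beyond 7 days | 0.84% | 0.504 | 0.802 | 89.3% |
| SAP example, all 9 days | 3.8% | 0.519 | 0.808 | 86.8% |
| Assumed | 5% | 0.525 | 0.81 | 85.6% |
| Assumed | 10% | 0.55 | 0.82 | 80.5% |

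At a true ratio of 1.0 there is no shift at any f. The power column only gives scale, since no formal test rests on these analyses.

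**4. Effect of removing gap time.** In simulation (1,000 trials each, gaps unrelated to VOC risk), the window as defined gave ratios of 0.524 and 0.551 at f = 5% and 10%. Dropping gap days together with their events returned 0.497 in both cases.

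**5. The tail after the common study end date (CSED).** SAP 3.1.4.1 ends the treatment period at the CSED, and SAP 3.2.1 leaves VOCs outside that period out of the primary analysis, which sensitivity analysis 1 repeats. For a child still dosing at the CSED, last dose + 7 days runs up to 7 days past it. With 365 days of follow-up this is 7/372 = 1.9% of the offset, and with 540 days it is 7/547 = 1.3%. Each arm's rate is understated by about that much, and the ratio hardly moves.

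**The case against.** Several points on the other side stand.

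- **Size.** The only interruption shown in the documents moves 0.50 to 0.504–0.519. The 5% and 10% rows are assumptions.
- **COVID-19.** A reader might infer that mandatory pandemic stops make the dilution large. The documents do not support that. Most stops in Protocol 3.9.2 are permitted rather than required, several at the investigator's discretion. The COVID-19 stop falls away if assessments can be done at home or locally. The rule came with protocol version 3.0 of 20 April 2020, and the SAP update of 26 June 2020 already reflects early termination, so only 67 days lie between them. A stop still running at termination is cut at 7 days.
- **Other analyses.** A reader might also infer that no other analysis addresses children who took the drug as planned. Sensitivity analysis 4 repeats the primary analysis in the per-protocol set. It selects patients on important deviations, and its detailed rules are in a separate plan. The SAP sections on it do not describe removing interruption time within a patient, so it narrows the gap without closing it.
- **Visibility.** SAP 4.2.5 tabulates interruptions, their reasons and the missed days by treatment group, with COVID-19 days shown separately. A reader can see that dilution is possible but cannot correct for it.
- **Informative gaps.** Stops for illness or surgery may be related to VOC risk, so deleting that time can introduce its own bias. The permanent stops already removed share this weakness. It is a reason to report a second version beside the planned one, not to replace it.
- **Imputation.** Appendix E splits each patient once, into counts before and after withdrawal. Removing interior gaps leaves open whether they are imputed and at which rate.

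**Conclusion.** The mismatch is real and follows from the text: a window that includes restarted gaps cannot represent everyone staying on treatment. The pull toward 1 is conditional. It needs a drug that works, an effect that fades during gaps, and dosing that resumed. Under those conditions the shift is (1 − RR) × f, negligible for short stops and 0.05 at a true 0.50 if f reaches 10%. The value of f has to come from the trial data.

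A reader might infer that the main result is biased. It is not: the primary analysis is treatment-policy and counts off-drug time by design. Nor does the post-CSED tail bias the comparison to any useful degree, because it lengthens the offset in much the same way in both arms. The point concerns supplementary analyses only, but it is worth settling because these are the analyses a reader will use to judge whether interrupted treatment explains the primary result.

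**What to change.** Before unblinding:

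1. Keep SAP 3.1.7.1 unchanged for safety tabulation.
2. For sensitivity analysis 1 and the direct-likelihood efficacy estimand in Appendix E, add a version in which on-treatment time is the union of the EX eCRF dosing intervals, each extended by 7 days or to the restart if that comes first. Apply it to both the VOC count and the offset.
3. Cap every on-treatment efficacy window at the end of the defined treatment period.
4. For the Appendix E imputation analyses, state whether gap time is excluded or imputed and, if imputed, at which arm's rate under each assumption.
5. Report the planned and added versions side by side, with the observed share of window time in gaps by arm.

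The cost is SAP wording and some programming, with no new data, since the interruption dates are already used to derive actual exposure. The imputation rule in item 4 needs the most thought. The added version has slightly less follow-up and is open to bias if gaps are informative, which is why both should be shown.

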3.1.7.2 Off-treatment Period

The off-treatment period follows the end of the on-treatment period, 1 day after the “last dose of study treatment + 7 days” as defined in Section 3.1.7.1.

3.1.8 Retests and Unscheduled Assessments

By-visit summaries will be presented by scheduled eCRF visit (number and name) and no analysis visit windowing will be applied. Unscheduled assessments will only be listed and will not contribute to these by-visit summaries. Results from unscheduled laboratory, vital signs and ECG assessments will, however, be included in the identification of maximum and/or minimum values as well as in the identification of any treatment-emergent abnormalities or changes.

3.2 Primary Efficacy Variable

3.2.1 Vaso-occlusive Crises (VOCs)

A VOC event occurring during the study (following randomisation at Visit 2) and, as judged by the investigator to fulfil the definition of the primary endpoint event, should be recorded by the investigator both as a primary endpoint event on the VOC1 eCRF and as an adverse event (AE) on the AE eCRF.

The primary efficacy variable is the number of VOC events during the treatment period. The number of VOC events is defined as the count of VOC events experienced by a patient over the defined treatment period (refer to Section 3.1.4), as assessed by the investigator and collected on the VOC1 eCRF. Any VOC event identified outside the defined treatment period will not be included in the primary analysis.

A VOC is the composite of a painful crisis and/or an acute chest syndrome (ACS) event.

Each component is defined as:

- A painful crisis is an onset or worsening of pain that lasts at least 2 hours, for which there is no explanation other than vaso-occlusion and which requires therapy with oral or parenteral opioids, parenteral non-steroidal anti-inflammatory drugs (NSAIDs), or other analgesics prescribed by a healthcare provider in a medical setting (such as a hospital, clinic or emergency room visit) or at home.

- ACS is an acute illness characterised by fever and/or respiratory symptoms, accompanied by a new pulmonary infiltrate on a chest X-ray.

A VOC event is identified as follows:

- Within each of the two separate components: Event with an onset date ≤ 7 days of the previous event onset date will not be counted as a new event. It will be composed of the start date of the first occurrence of the component in the event to the stop date of the last occurrence of the component in the event.

For example: Patient 1: *Counted as 2 events not 3 individual events*

PAINFUL CRISIS	2019-07-24	2019-07-28
PAINFUL CRISIS	2019-10-22	2019-10-23
PAINFUL CRISIS	2019-10-28	2019-10-30

- Across the two separate components: Event with an onset date ≤ 7 days of the previous event onset date will not be counted as a new event. It will be composed of the start date of the first component in the event to the stop date of the last component in the event.

For example: Patient 2: *Counted as 4 events not 5 individual events*

ACUTE CHEST SYNDROME	2019-07-17	2019-07-23
PAINFUL CRISIS	2019-07-17	2019-07-23
PAINFUL CRISIS	2019-10-04	2019-10-04
PAINFUL CRISIS	2019-10-21	2019-11-05
PAINFUL CRISIS	2019-12-12	2019-12-12

3.3 Secondary Efficacy Variables

The secondary efficacy variables are:

- Number of painful crises
- Duration of painful crises

- Number of ACS events
- Number of VOC events requiring hospitalisation or emergency department visits
- Number of days hospitalised for VOC events
- Number of acute SCD complications
- Number of days hospitalised for acute SCD complications
- Number of sickle cell-related red blood cell (RBC) transfusions
- PedsQL SCD Module and PedsQL Multidimensional Fatigue Scale Scale: Total score and by dimension
- Proportion of days absent from school or work due to SCD
- Intensity of worst daily VOC-related pain (during VOC events)
- Analgesics administered for VOC events (opioids/non-opioids)
- Swallowability and palatability

